10.1.5 Analysis of Psoriasis Symptoms Scale (PSS)

The 4-item PSS was designed to measure patient-reported psoriasis symptoms. Subjects are requested to rate the severity of each of their symptoms related to pain, redness, itching, and burning, in the last 24 hours from "0 = none" to "4 = very severe," with total scores, which is the sum of the four item responses, ranging from 0 to 16 with higher scores indicating worse symptoms. If one or more of the four items are missing then the total score for that day will be set to missing.

PSS will be completed on Day 1 and the Week 16 visit in Part A. Total Score from Day 1 will be used as the baseline value. Change from baseline in PSS will be analyzed by the van Elteren test between the risankizumab arms and placebo arm using the stratification factors of Concomitant PsA at baseline (Yes: Diagnosed or Suspected; versus: No) and body weight (≤ 90 kg versus > 90 kg). An example of the SAS code for this is as follows:

```
proc freq data = indata;  
  
tables strata * treatment * aval1 / cmh2 scores=modridit nopol;
```

where "strata" is numbered 1 – 4 based on the row order, "treatment" is dichotomous (Arm A or Arm B), and "aval1" is the PSS change from baseline at Week 16. In the output from this code, the p-value is the "Prob" for statistic 2 – "Row Mean Scores Differ."

PSS will be completed by the subject during clinic visits at Week 28, Week 40 and Week 52 in Part B. The PSS change from baseline will be summarized for these visits for each treatment arm.

In addition to the PSS total score, the four individual components, pain, redness, itching, and burning, will be analyzed using the same methodology.

10.2 Primary Efficacy Analysis

The primary hypotheses is that either risankizumab 150 mg or risankizumab 75 mg is superior to placebo in achieving $\geq 90\%$ reduction from baseline in the PASI score (PASI 90) at Week 16 in participants with moderate to severe chronic plaque psoriasis.

In order to maintain the full significant level of 5%, the following null hypotheses will be tested in rank order, with two-sided alpha level 0.05.

1. Risankizumab 150 mg is not different from placebo with respect to PASI 90 response at Week 16

2. Risankizumab 75 mg is not different from placebo with respect to PASI 90 response at Week 16

The difference in proportion of subjects achieving PASI 90 between treatment arms will be estimated and tested using the Cochran-Mantel-Haenszel risk difference estimate stratified by the stratification factors of Concomitant PsA at baseline (Yes: Diagnosed or Suspected; versus: No) and body weight (≤ 90 kg versus > 90 kg).

The primary analysis will be carried out in the ITT Population and the PP Population. Non-responder imputation will be used as the primary approach for missing values. LOCF and MI will be performed as sensitivity analyses.

10.3 Secondary Efficacy Analyses

Secondary endpoints will be analysed in the ITT Population. The same methods as discussed for the primary analyses will be used to analyze all binary secondary endpoint at Week 16.

Secondary endpoints for Week 52 will be summarized descriptively.

Secondary Efficacy Endpoints are:

- Achievement of PASI 90 at Week 52
- Achievement of an sPGA score of clear or almost clear at Week 16
- Achievement of an sPGA score of clear or almost clear at Week 52
- Achievement of $\geq 75\%$ reduction from baseline PASI score (PASI 75) at Week 16
- Achievement of PASI 75 at Week 52
- Achievement of 100% reduction from baseline PASI score (PASI 100) at Week 16
- Achievement of PASI 100 at Week 52

- Achievement of an American College of Rheumatology (ACR) 20 response at Week 16, among subjects with confirmed diagnosis of PsA using CASPAR criteria and with baseline total TJC and SJC counts ≥ 3 at selected study sites
- Achievement of an ACR 20 at Week 52, among subjects with confirmed diagnosis of PsA using CASPAR criteria and with baseline total TJC and SJC counts ≥ 3 at selected study sites

10.3.1 Further Efficacy Analysis

Further exploratory endpoints below will be analyzed among the ITT Population at all visits collected:

- Achievement of PASI 50/75/90/100
- Achievement of sPGA of clear and sPGA of clear or almost clear
- Time until the first achievement of PASI 50, PASI 75, PASI 90, PASI 100, sPGA of clear and sPGA of clear or almost clear
- Time until loss of PASI 75, PASI 90, PASI 100, sPGA of clear and sPGA of clear or almost clear response
- Change from baseline in PASI score
- Percent change from baseline in PASI
- Achievement of absolute PASI of < 3
- Change from baseline in psoriasis symptoms evaluated using the total score on the Psoriasis Symptoms Scale (PSS)
- Achievement of a Dermatology Life Quality Index (DLQI) score of 0 or 1
- Achievement of total score on the PSS of 0
- Change from baseline in DLQI
- Change from baseline in HAQ-DI, among subjects with confirmed diagnosis of PsA using CASPAR criteria and with baseline total TJC and SJC counts ≥ 3 at selected study sites
- Change from baseline in Pain VAS, among subjects with confirmed diagnosis of PsA using CASPAR criteria and with baseline total TJC and SJC counts ≥ 3 at selected study sites

- Change from baseline in Patient's Global Assessment VAS, among subjects with confirmed diagnosis of PsA using CASPAR criteria and with baseline total TJC and SJC counts ≥ 3 at selected study sites
- Change from baseline in Investigator's Global Assessment VAS, among subjects with confirmed diagnosis of PsA using CASPAR criteria and with baseline total TJC and SJC counts ≥ 3 at selected study sites
- Achievement of an ACR 20, among subjects with confirmed diagnosis of PsA using CASPAR criteria and with baseline total TJC and SJC counts ≥ 3 at selected study sites
- Investigator's global assessment among subjects with confirmed diagnosis of PsA using CASPAR criteria and with baseline total TJC and SJC counts ≥ 3 at selected study sites
- Change from baseline in CRP, among subjects with confirmed diagnosis of PsA using CASPAR criteria and with baseline total TJC and SJC counts ≥ 3 at selected study sites
- Change from baseline in TJC and SJC, among subjects with confirmed diagnosis of PsA using CASPAR criteria and with baseline total TJC and SJC counts ≥ 3 at selected study sites

In addition, the proportion of subjects achieving PASI 90, PASI 100, sPGA of clear, and sPGA of clear or almost clear at each visit in Part B will be summarized among those who had PASI 90, PASI 100, sPGA of clear, and sPGA of clear or almost clear, respectively, at the entry of Part B.

10.4 Handling of Multiplicity

The statistical comparisons for the primary efficacy will be carried out in the hierarchical order:

1. The risankizumab 150 mg groups vs the placebo group.
2. The risankizumab 75 mg groups vs the placebo group.

The statistically significant results (p -value ≤ 0.05) for the comparison in the higher rank are necessary to initiate the testing of the next comparison in the lower rank. Since a step-down procedure is used, each comparison will be tested at a significance level of 0.05 and overall alpha level of 0.05 will be preserved.

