10.0 Efficacy Analysis

10.1 General Considerations

When the last patient completes the Week 28 visit, the Primary Analysis will be performed including all efficacy endpoints pertaining to Part A. This is the only and final analysis for these endpoints, hence no alpha adjustment is required. For this primary analysis, all endpoints will be analysed up to Week 28, with the following exception:

- Categorical endpoints related to PASI and sPGA, using the LOCF method, will be analysed up to the last visit that at least one subject has observed PASI and sPGA measurements, respectively.

The treatment effect will be evaluated based on a two-sided significance level of 0.05 (when rounded to three decimal places).

The ITT population will be used for the analyses of efficacy endpoints. The following treatment periods will be analyzed:

- Part A (up to Week 16)
- Part B (Week 16 and after)

Time-to-event analysis will be performed across the entire study for subjects who are randomized to risankizumab or placebo arms in addition to the analyses in Part A.

Primary variable will also be analyzed for the per-protocol populations using primary approach to handle missing data as described in Section [10.1.4](#).

Subjects' actual Concomitant PsA at baseline (Yes: Diagnosed or Suspected; versus: No) and body weight (≤ 90 kg versus > 90 kg) will be used as the strata in the stratified analyses.

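### The fixed test sequence stops at PASI 90, so no Week 16 secondary result can support an error-controlled claim; adding the six skin tests below it costs the primary nothing

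*SAP*

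**What the plan says.** Protocol 7.1 describes the trial as confirmatory, and protocol 2.1 says that it is meant to support registration in Japan.

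- **Sequence.** SAP 10.4: "The statistical comparisons for the primary efficacy will be carried out in the hierarchical order", with 150 mg against placebo first and 75 mg second. It adds that "each comparison will be tested at a significance level of 0.05 and overall alpha level of 0.05 will be preserved". Protocol 7.2 and SAP 10.2 state null hypotheses for PASI 90 at Week 16 only.
- **Week 16 secondaries.** SAP 10.3: "The same methods as discussed for the primary analyses will be used to analyze all binary secondary endpoint at Week 16". Protocol 7.3.2 agrees. That method (protocol 7.3.1, SAP 10.1.1) gives a stratified risk difference, a 95% confidence interval and a p-value. The endpoints are sPGA 0/1, PASI 75, PASI 100 and, in a psoriatic arthritis subset at selected sites, ACR 20.
- **Week 52 secondaries.** "Secondary endpoints for Week 52 will be summarized descriptively" (SAP 10.3).
- **Level.** SAP 10.1: "The treatment effect will be evaluated based on a two-sided significance level of 0.05".

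Neither document orders or adjusts the Week 16 secondary tests, or says that their p-values are nominal.

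**The concern.** The plan separates Week 16 secondaries, which are tested, from Week 52 secondaries, which are descriptive. It then leaves the tested ones outside any error control. Four endpoints at two doses give eight comparisons against one shared placebo arm. A reader of the report would see eight p-values next to a 0.05 threshold in a confirmatory trial, with nothing to say how a value below it should be read.

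What is at stake is what the trial can conclude beyond PASI 90. As written, clear or almost clear skin, PASI 75 and complete clearance at Week 16 can only be supportive. The same tests, placed below PASI 90 in the existing sequence, could carry claims with familywise error held at 0.05.

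**Working it through.** **1. The plan's own figure.** Protocol 7.7 gives 17 per arm for 95% power at 65% versus 5%, two-sided 0.05. With mean rate 0.35:

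n = [1.960·√(2·0.35·0.65) + 1.645·√(0.65·0.35 + 0.05·0.95)]² / 0.60² = 13.26, so 14 per arm.

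With continuity correction: (13.26/4)·[1 + √(1 + 4/(13.26·0.60))]² = 16.4, so 17. The figure reproduces. At the actual 56 per arm, power for both PASI 90 tests exceeds 99.9%.

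**2. Number of tests.** Skin endpoints: 3 × 2 doses = 6. With ACR 20: 4 × 2 = 8.

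**3. Chance of at least one false positive if every secondary null is true.**
- Independent tests: six give 1 − 0.95⁶ = 26.5%; eight give 1 − 0.95⁸ = 33.7%.
- Six skin tests, normal approximation, correlation 0.5 between doses (shared placebo, equal arms): 25% when the endpoint statistics are uncorrelated, 21% at correlation 0.6, 15% at 0.9.
- Six skin tests, binomial simulation (56 per arm, unstratified Wald test, latent correlation 0.6 to 0.9): 18-21% at assumed null rates of 7%, 10% and 1% for sPGA 0/1, PASI 75 and PASI 100; 24-27% at 10%, 20% and 5%.
- If the dose order is taken to apply within each endpoint, four families at 0.05 remain: at most 1 − 0.95⁴ = 18.5% if independent.

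The documents give no Week 16 rates for the secondary endpoints, so these rates and correlations are assumptions. A fair summary for the six skin tests is roughly 15-27%.

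**4. Cost of extending the sequence.** Tests placed below PASI 90 cannot change its power. For the rest, exact Fisher power per test at 56 per arm (unstratified, as a stand-in for the stratified test):

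| Endpoint | Active vs placebo | Power per test |
|---|---|---|
| PASI 75, sPGA 0/1 | 65% vs 20% | 99.8% |
| PASI 100 | 29% vs 1% | 99.6% |
| PASI 100 | 25% vs 1% | 98% |
| PASI 100 | 20% vs 1% | 92% |
| PASI 100 | 20% vs 3% | 76% |

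For PASI 75, 65% is a floor under the plan's own assumption, because every PASI 90 responder is also a PASI 75 responder. For sPGA 0/1 it is an assumption, as are all the placebo rates. The 29% is the only PASI 100 figure in the documents (protocol 1.2): a single-dose phase I result at Week 24, pooled over routes.

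Lower bound for passing a chain = 1 − sum of (1 − power):
- PASI 90, sPGA 0/1 and PASI 75, both doses: 1 − 4·0.0019 = 99.2%.
- With PASI 100 at 29% vs 1%: 1 − 0.0076 − 2·0.0039 = 98.5%.
- At 25% vs 1%: 1 − 0.0076 − 2·0.0169 = 95.9%.
- At 20% vs 1%: 1 − 0.0076 − 2·0.0804 = 83.2%.

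**5. ACR 20 is different.** The subset size is not stated. Protocol 1.1 gives 30% joint involvement as general background. Taken as an upper bound, 0.30 × 56 is about 17 per arm. At an assumed 50-60% versus 20%, simulated power per test is 0.46-0.70 with 17 per arm and 0.28-0.45 with 8. Gating 75 mg behind 150 mg lowers the 75 mg power to 0.28-0.55 and 0.12-0.26.

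**The case against.** The strongest reply is that this is a choice of scope. Hypotheses, power and the claim of alpha control are all confined to PASI 90, and that claim is sound. Whether any secondary endpoint should be confirmatory is the sponsor's decision, and one sentence calling secondary p-values nominal would remove the ambiguity. This stands: the plan makes no false statement.

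The global null is also hard to believe. At the planned 65% versus 5% for PASI 90, a true null for PASI 75 would need a placebo PASI 75 rate of at least 65%. If PASI 90 is null too, the primary will usually fail and secondary claims are unlikely to be pressed. In one simulation under that null (assumed rates: sPGA 0/1 7%, PASI 75 10%, PASI 90 5%, PASI 100 1%; latent correlation 0.9), a significant 150 mg primary result together with any significant skin secondary occurred about 3% of the time, against 19% for any skin secondary alone. This also stands, and it makes the point an improvement rather than an error.

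Third, SAP 10.3 sets no level of its own, and its reference to the primary methods could be read as importing the dose order. That is arguable, but SAP 10.4 names only the primary, and four unprotected families would remain.

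A reader might infer more than the documents support:
- *That the trial's type I error is inflated.* It is not, for the primary claim.
- *That all eight tests could join the sequence at almost no cost.* That fails for ACR 20, and for PASI 100 if its active rate is nearer 20%.
- *That the false-positive risk is about one in three.* The 33.7% assumes eight independent tests with every null true.

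**Conclusion.** The gap is real but limited. The two PASI 90 comparisons are controlled at 0.05. The Week 16 secondary tests lie outside the sequence under a general 0.05 level, so as written none can support an error-controlled claim. The 15-27% for the six skin tests describes a global null that is unlikely if the drug works; it measures the missing control and is not a forecast of false findings.

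The case for acting is that the protection is cheap. It costs PASI 90 nothing and is negligible for sPGA 0/1 and PASI 75 even at a pessimistic 65% versus 20%. For PASI 100 the cost depends on rates that the documents do not give, which is why it belongs last. ACR 20 belongs outside the sequence.

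**What to change.** In SAP 10.4 and protocol 7.2, before unblinding for the Week 28 analysis, continue the sequence after the two PASI 90 tests. All tests are at Week 16, two-sided 0.05, and each is made only if all earlier ones succeed:

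1. sPGA 0/1: 150 mg, then 75 mg
2. PASI 75: 150 mg, then 75 mg
3. PASI 100: 150 mg, then 75 mg

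State in SAP 10.3 and 10.1 that p-values for ACR 20 and all other efficacy comparisons are nominal. If the sponsor wants no secondary claims, the minimum is one sentence calling every secondary p-value nominal.

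The cost is one paragraph in each document. The downside is that an early failure blocks every later claim. At the assumed rates this is unlikely before PASI 100, and a failure there blocks only what remains of PASI 100.

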10.5 Efficacy Subgroup Analysis

To evaluate the consistency of the efficacy on the primary endpoint of PASI 90 at Week 16 over demographic and other baseline characteristics, summaries and analyses will be performed for the following subgroups.

- Age (< 40 years, $\geq 40 - < 65$ years, ≥ 65 years)
- Sex (male, female)
- Smoking (current, ex or never)
- BMI (normal: < 25, over weight: $\geq 25 - < 30$, obese: ≥ 30);
- Body weight (≤ 90 kg versus > 90 kg)
- Body weight (\leq median versus $>$ median)
- Baseline PASI score (by median);
- Baseline sPGA (3, 4)
- concomitant PsA at baseline (Yes: baseline total TJC and SJC counts ≥ 3 versus No: otherwise) among the subjects at the selected sites
- Psoriasis Therapy History (Phototherapy or Photochemotherapy, TNF Antagonist, Other biologics, Non-biologic systemic therapy, All biologics, Naïve to all)

11.0 Safety Analysis

11.1 General Considerations

Safety analyses will include adverse events, laboratory, local tolerability, ECG, and vital sign measurements. Safety summaries will be provided using the safety population as defined in Section 5.1. Pairwise comparisons of risankizumab vs placebo will be

performed in the Safety Population. Continuous variables will be analyzed using one-way ANOVA and categorical variables will be analyzed using Fisher's exact test. For analyses of AEs, only P values ≤ 0.100 , when rounded to three digits, will be presented.

Missing safety evaluations will not be imputed.

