7.1 Demographic and Baseline Characteristics

Demographic and baseline characteristics will be summarized for each arm and for overall of the ITT population. The number of observations, mean, standard deviation, median, minimum and maximum will be summarized for continuous variables; and treatment groups will be compared using a one-way analysis of variance (ANOVA) model with treatment as the independent factor. Categorical or discrete variables will be summarized via counts and percentages; and treatment groups will be compared using a two-sided Pearson's Chi-Square test (or an appropriate exact test if expected cell count < 5).

The following demographic and baseline parameters will be summarized.

Subject Demographics

- Sex (male, female)
- Age (years), defined as the number of years from date of birth to date of first drug
- Age (< 40 years, \geq 40 – < 65 years, \geq 65 years)
- Body weight (kg)
- Body weight category (\leq 90 kg versus $>$ 90 kg).
- Height (cm)
- BMI (kg/m^2)
- BMI (normal: < 25, over weight: \geq 25 – < 30, obese: \geq 30);
- concomitant PsA at baseline

General Baseline Characteristics

- PASI (Psoriasis Area and Severity Index)
- sPGA categories
- BSA (Body Surface Area)
- PSS
- Dermatology Life Quality Index (DLQI)
- HAQ-DI (HAQ Disability Index)
- Pain VAS (Visual Analog Scale)/Patient Global Assessment (PtGA) VAS (Visual Analog Scale)
- TJC/SJC (Tender/Swollen Joints)
- Investigator's Global Assessment VAS
- Serum CRP

Psoriasis and Cardiovascular History

- Psoriatic arthritis (diagnosed, suspected, no)
- Cardiovascular Diseases (myocardial infarction, angina pectoris, transient ischemic attack, stroke, deep vein thrombosis)

- Cardiovascular Risk Factors (hypertension, hyperlipidemia, diabetes mellitus, obesity)

General Use

- Smoking history (Never-smoked, Ex-smoker, Currently smokes)
- Alcohol History (Non-drinker, drinks – no interference to study participation, drinks – possible interference to study participation)

Prior Treatment:

- Psoriasis TNF antagonist and Other Biologic Usage History – by Response to Treatment
- Psoriasis Treatment – by Therapy Type (topical therapy, phototherapy, photochemotherapy, non-biologic systemic therapy, TNF antagonist, other biologic)

Physical Exam, Infection screening and Pregnancy Test will be presented in listing format.

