10.1.2 Analyses of Continuous Variables

Change from baseline in PSS will be analyzed by stratified van Elteren test. For other continuous variables, the model based mean and standard error will be presented. The Baseline and visit means will also be presented for each treatment group for subjects who

have both Baseline and post Baseline visit values. The treatment groups will be compared using ANCOVA with treatment group, Baseline value, and stratification factors in the model.

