11.3.2 Statistical Methods

All analyses will be conducted in the Safety Population. Table for potentially clinically important lab values will also be summarized in the ALL_RZB Population.

Analysis of Continuous Laboratory Parameters

Though the protocol indicates utilizing the Rheumatology Common Toxicity Criteria (RCTC) scale for grading laboratory values, given that the NCI National Cancer Institute Common Toxicity Criteria for Adverse Event (CTCAE) scale includes a more comprehensive list of laboratory values; therefore, the lab analyses based on the NCI CTCAE scale will be presented. Change from Baseline to each scheduled visit and to the final value in continuous laboratory parameters will be summarized with the mean, standard deviation and median. The Baseline and visit/final value means will also be presented for subjects who have both the Baseline and visit/final values (see Section 6.0 for the definition of Baseline and final values). If there are multiple post-baseline measurements on the same day, the average value will be used.

Shift Tables

Shift tables for changes from Baseline according to the normal range will be provided for each hematology and clinical chemistry parameter. Shifts from Baseline to the following endpoints will be considered: minimum value, maximum value and final value. Categories of "low or normal" and "high or normal" will be included at Baseline in addition to the categories of "low," "normal," "high" and "missing." If there are multiple measurements on the same day, the last value will be used.

Potentially Clinically Important Laboratory Values

Frequencies and percentages of subjects with post Baseline lab values meeting the following criteria will be summarized. Of note, a post baseline value must be more extreme than the baseline value to be considered a potentially clinically important finding.

Table 12. Criteria for Potentially Clinically Important Chemistry Values

Chemistry Variables	Units	Definition of Potentially Clinically Important Current (Version 4) NCI CTCAE Grade 3 or Greater	
		Very Low	Very High
TBL	mcmol/L		> 3.0 × ULN
SGOT/AST	U/L		> 5.0 × ULN
SGPT/ALT	U/L		> 5.0 × ULN
Albumin	g/L	< 20	
Glucose	mmol/L	< 2.2	> 13.9
Triglycerides	mmol/L		> 5.7
Creatinine	mcmol/L		> 3.0 × ULN
Sodium	mmol/L	< 130	> 155
Potassium	mmol/L	< 3.0	> 6.0
Calcium	mmol/L	< 1.75	> 3.1
CPK	U/L		> 5.0 × ULN
Total Cholesterol	mmol/L		> 10.34
GGT			> 5.0 × ULN
ALP			> 5.0 × ULN
Lipase			> 5.0 × ULN
Amylase			> 5.0 × ULN

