11.4.2 Statistical Methods

Changes from Baseline to each visit and to the final value in vital sign parameters will be summarized with the mean, standard deviation and median. The Baseline and final value means will also be presented for subjects who have both the Baseline and final values (see Section 6.0 for the definition of Baseline and final values).

For baseline, if there are multiple measurements on the same day, the last measurement prior to the first dose of study drug will be used as the Baseline vital sign value. If there are multiple post-baseline measurements on the same day, average value will be used.

For systolic blood pressure, diastolic blood pressure and pulse, a listing of all subjects with any vital sign value meeting criteria for potentially clinically important values will be provided. For each of these subjects, the whole course of the respective parameter will be listed. The number and percentage of subjects who have at least one value meeting criteria for potentially clinically important values will be provided for each selected vital sign parameter.

All analyses will be conducted in the Safety Population. Table for potentially clinically important vital signs will also be summarized in the ALL_RZB Population.

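### Part A laboratory and vital-sign changes are compared with placebo by one-way ANOVA without the baseline value, which gives up some precision in descriptive safety contrasts (optional, low priority)

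*SAP*

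**What the plan says.** SAP 11.1 sets the general rule for safety: "Pairwise comparisons of risankizumab vs placebo will be" carried out in the Safety Population, and "Continuous variables will be analyzed using one-way ANOVA". It names no covariate. SAP 7.1 describes the same method for baseline characteristics as a "one-way analysis of variance (ANOVA) model with treatment as the independent factor", so the term as used in this SAP means treatment only.

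The quantities are given further on. SAP 11.3.2: "Change from Baseline to each scheduled visit and to the final value in continuous laboratory parameters will be summarized" by mean, standard deviation and median. SAP 11.4.2: "Changes from Baseline to each visit and to the final value in vital sign parameters will be summarized" in the same way. Neither section adds a covariate or repeats the comparison method. SAP 6.0 defines a baseline for safety analyses, so the value is available for each patient measured before dosing.

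For continuous efficacy variables other than PSS, SAP 10.1.2 says: "The treatment groups will be compared using ANCOVA with treatment group, Baseline value, and stratification factors in the model".

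Protocol 7.3.4 describes the safety analyses as generally descriptive and plans no hypothesis tests. Protocol 3.2 notes that only the first 16 weeks allow a direct comparison of adverse events with placebo, because placebo patients then switch to active drug. The contrasts at issue are therefore those of Part A.

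**The concern.** A change score subtracts the whole baseline value. Unless follow-up tracks baseline perfectly, that over-corrects: patients with high baselines tend to fall and those with low baselines tend to rise, whatever the treatment. This adds noise to the comparison of mean changes. Entering baseline as a covariate removes it. The value is already collected, and the same SAP already uses it this way for efficacy.

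What is at stake is precision in the trial's only randomised placebo-controlled comparison of laboratory and vital-sign changes, which has 56 patients per arm and lasts 16 weeks.

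**Working it through.** **Inputs.** 56 patients per arm in Part A (protocol 7.7, SAP 4.3), so each dose-versus-placebo contrast is 1:1. The documents give no SD, correlation or precision target for any safety variable, so there is no stated figure to reproduce. The 17 per arm in protocol 7.7 concerns PASI 90 and does not enter here. Assumptions: equal SD at baseline and follow-up, a linear relation with a common slope, and rho taken over a range.

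**Formulas**, in units of the SD, with n = 56 per arm:
- ANOVA on change: SE = sqrt(2(1 − rho) × 2/n)
- ANCOVA with baseline: SE = sqrt((1 − rho²) × 2/n)
- Variance ratio: (1 − rho²) / (2(1 − rho)) = (1 + rho)/2

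| rho (assumed) | SE, ANOVA on change | SE, ANCOVA | Variance ratio | Fall in SE | n per arm giving ANOVA the same precision |
|---|---|---|---|---|---|
| 0.3 | 0.224 | 0.180 | 0.65 | 19% | 56/0.65 = 86 |
| 0.5 | 0.189 | 0.164 | 0.75 | 13% | 56/0.75 = 75 |
| 0.7 | 0.146 | 0.135 | 0.85 | 8% | 56/0.85 = 66 |
| 0.9 | 0.085 | 0.082 | 0.95 | 2.5% | 56/0.95 = 59 |
| 0.95 | 0.060 | 0.059 | 0.975 | 1% | 56/0.975 = 57 |

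**Cost of estimating the slope.** With all three arms in the model (168 patients) the ANCOVA variance rises by a factor of about 1 + 1/(168 − 5) = 1.006. Break-even is where (1 + rho)/2 × 164/163 = 1, that is rho = 2 × 163/164 − 1 = 0.988. With two arms per model (112 patients) the factor is about 1 + 1/108, and break-even is 2 × 108/109 − 1 = 0.982. The gain is therefore gone at rho of about 0.98 to 0.99.

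**Simulation.** In 6,000 simulated three-arm trials at each rho, the variance ratios were 0.754, 0.879 and 0.964 at rho 0.5, 0.7 and 0.9. The formula with the slope cost gives 0.755, 0.855 and 0.956. The middle value is somewhat high; three repeats of 20,000 trials at rho 0.7 gave 0.854, 0.859 and 0.852, so this is simulation error.

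**Baseline imbalance.** The SE of a baseline difference is sqrt(2/56) = 0.189 SD, so an imbalance of 0.2 SD is an ordinary chance result. At rho 0.6 it moves the change-score contrast by (1 − 0.6) × 0.2 = 0.08 SD. The SE of that contrast is sqrt(2 × 0.4 × 2/56) = 0.169 SD, so the shift is 0.08/0.169 = 0.47 of one SE. That variation is already inside the ANOVA interval. It is the lost precision seen from another side, not an additional harm.

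**If raw visit values were analysed instead of changes**, the variance ratio would be 1 − rho²: 0.75 at rho 0.5 and 0.19 at rho 0.9. Under that reading the loss would be at least as large from rho 0.5 upward, and much larger at high rho.

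**The case against.** **Safety is descriptive.** Protocol 7.3.4 plans no safety tests, so no decision, sample size or power figure depends on these standard errors. This stands and sets the priority. It does not remove the point, because SAP 11.1 still plans the comparisons with placebo, and a descriptive difference is more useful when it is more precise.

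**The use of change scores is inferred.** Correct. SAP 11.1 speaks only of continuous variables; 11.3.2 and 11.4.2 say that changes are summarised. Reading them together is reasonable, and the alternative reading does not help the plan.

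**Baseline is already considered where signals are sought.** Potentially important values must be more extreme than baseline, shift tables start from the baseline category, and baseline means are shown next to visit or final means. This also stands: mean-change contrasts are only one part of the safety review, and an imbalance would be visible.

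**ANCOVA is not free of assumptions.** It needs a roughly linear relation and a common slope. Parameters such as CK, CRP, triglycerides and liver enzymes may be strongly skewed, and extreme baselines could then have high leverage. This is a small but real downside.

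A reader might go further and infer that a chance imbalance makes the planned contrast biased, or that it could pass for a drug effect. The documents do not support that: the arms are randomised, the change-score contrast is unbiased over randomisations, and its interval already allows for the imbalance. Nor does the ANCOVA in SAP 10.1.2 make the safety rule a contradiction. That section covers efficacy, exempts PSS, and a simpler model for descriptive safety output is a permissible choice.

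**Conclusion.** The point holds as a modest loss of precision. The planned Part A comparison is valid, but with baseline as a covariate its standard error would be about 13%, 8% or 2.5% smaller at rho 0.5, 0.7 or 0.9, with essentially nothing to gain for parameters that track baseline almost perfectly. These figures rest on assumed correlations, equal SDs, a linear common slope, 56 patients per arm with data, and the inference that the ANOVA is run on change. One should not infer that every parameter is materially affected or that any stated conclusion of the trial is at risk. It is an optional, low-priority improvement.

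**What to change.** In SAP 11.1, for Part A change from baseline in laboratory and vital-sign variables, replace one-way ANOVA by ANCOVA with treatment and the baseline value. State explicitly that change from baseline is the response. For each dose versus placebo, report the adjusted mean difference with a 95% CI, labelled as a descriptive estimate so that SAP 11.1 agrees with protocol 7.3.4. Allow a log scale for strongly skewed parameters, chosen before unblinding.

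The cost is one model statement in the SAP and the matching program change, plus the linearity and common-slope assumption noted above. No new data are needed.
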